8.1. Good Clinical Practice

Study personnel will have the appropriate qualifications related to education, training, and experience to perform study-related tasks. The study personnel will conduct the study in accordance with Good Clinical Practice (GCP), institutional review board (IRB), local and institutional guidelines.

8.2. Institutional Review Board

Prior to study initiation, the study investigator(s) will have written approval from the IRB for the protocol, consent form, and standardized written information that the study staff will provide to patients.

8.3. Informed Consent

Patients will be informed about the study and its purpose when a diagnostic nasopharyngeal swab for CARV is obtained. Eligible patients who have a positive swab result or a positive bronchoscopy specimen PCR for CARV will be approached by the study investigators. The consent process will involve a dialogue between the potential participant and the study staff. Study participation will require written informed consent from the patient. The study staff will not conduct study procedures prior to obtaining informed consent. Patients eligible for randomization will be informed that they may withdraw their consent and drop out of the study at any time point.

8.4. Adverse Events

8.4.1. Serious Adverse Event Definition

The protocol defines a serious adverse event (SAE) as any untoward medical occurrence that

- Results in death
- Threatens life (defined as an event in which the subject was at risk of death at the time of the event)
- Requires inpatient hospitalization or causes prolongation of an existing hospitalization
- Results in persistent or significant disability/incapacity
- Is a congenital anomaly or birth defect
- Results in the development of drug dependency or drug abuse
- Is a serious adverse event drug experience

All SAEs will be reviewed by the investigator to determine relationship to the study drug (definitely, likely or possibly related to the study product).

8.4.2. Site Adverse Event Collection

The study investigator and staff will monitor and evaluate for study participant SAEs. They will collect and record SAE information on the CRFs.

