4.1. Primary Aim

To conduct a single center, pilot, randomized placebo controlled trial that compares the efficacy and safety of inhaled beclomethasone versus placebo to prevent the development or progression of CLAD, or death after CARV infection in lung transplant recipients.

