4.3. Study Objectives

Primary Objective

- To determine if inhaled beclomethasone has greater efficacy than placebo in preventing the composite endpoint of new or progressive CLAD or death 6 months after CARV infection in adult lung transplant recipients.

Secondary Objectives

- Incidence of new or progressive CLAD at 6 and 12 months after CARV infection
- Time to development or progression of CLAD
- Safety and tolerability of inhaled beclomethasone
- Respiratory viral symptoms
- Development of donor-specific HLA antibodies (DSA)
- Change in DSA mean fluorescence intensity
- Development of antibodies to lung-specific self-antigens (Collagen V and K- α 1 tubulin)
- Serum cytokine profiles
- Peripheral immune cell phenotypes
- Incidence of other bacterial, viral, or fungal infection at the time of CARV infection
- Incidence of acute rejection and lymphocytic bronchiolitis within 6 months following CARV infection
- Survival at 6 months (+ 10 days) and 12 months (+ 10 days) after CARV infection

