4.9.2. Secondary Endpoints

Incidence of new and/or progressive CLAD, safety and tolerability of inhaled beclomethasone, respiratory virus symptom score, development of DSA, change in DSA mean fluorescence intensity, development of antibodies to

self-antigens, serum cytokine profiles, peripheral immune cell phenotypes, incidence of other bacterial, viral, or fungal pulmonary infections at the time of CARV infection, incidence of acute rejection and lymphocytic bronchiolitis within 6 months (+ 10) days after CARV infection, incidence of new or progressive CLAD within 12 months (+ 10) after CARV infection, and survival 6 months (+ 10 days) and 12 months(+ 10 days) after CARV infection.

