8.4.5. Discontinuation of Participants from Treatment

Study participants MUST discontinue study drug for any of the following reasons:

- Withdrawal of informed consent
- Any condition in which, in the opinion of the investigator, indicates that continued study drug treatment is not in the best interest of the patient.
- Termination of the study.
- Ineligibility for continued study drug treatment (Table 1)

Participants who discontinue study drug treatment should still comply with the protocol and undergo the study follow-up procedures, except for those who withdraw informed consent or become unable to freely participate in the ongoing informed consent process. CRF/computer data entry system will capture reason(s) for discontinuation and withdrawal.

9. Study Organization and Administration

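### Safety and tolerability is a named endpoint, but the plan records only serious adverse events, so non-serious effects in patients who stay on study drug have no planned record

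*Combined protocol and SAP*

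**What the plan says.** Section 4.1 (Primary Aim) sets up a trial that "compares the efficacy and safety of inhaled beclomethasone versus placebo". The Section 4.3 secondary objectives include "Safety and tolerability of inhaled beclomethasone", and Section 4.9.2 repeats this as a secondary endpoint without naming any component measure.

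Section 8.4 gives the data collection:

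- Section 8.4.1 defines serious adverse events. It does not define a non-serious one.
- Section 8.4.2 states: "The study investigator and staff will monitor and evaluate for study participant SAEs. They will collect and record SAE information on the CRFs".
- Section 8.4.3 requires a report for every SAE and mentions no other event.
- Section 8.4.4 leaves the handling of any AE to clinical practice and gives no recording instruction.
- Section 8.4.5 adds that the "CRF/computer data entry system will capture reason(s) for discontinuation and withdrawal".

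Section 7 assigns generic tests to secondary endpoints (chi-squared for categorical data, t-test or Mann-Whitney for continuous data) and names no safety or tolerability variable.

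**The concern.** The plan names an endpoint and does not say which data feed it. An adverse effect that is bothersome but not serious meets none of the SAE criteria in Section 8.4.1 (death, threat to life, hospitalization, lasting disability and the like). If the patient also keeps taking study drug, nothing in Section 8.4 requires anyone to write the effect down.

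Treatment lasts 180 days, and the trial calls itself a pilot. A description of how patients tolerate the drug is one of the more useful things a pilot can deliver. Events that are not recorded when they happen cannot be reliably reconstructed later, so the gap has to be closed before patients are treated.

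**Working it through.** The plan states no figure on this point, so there is none to reproduce. The check is textual, followed by a short illustration of size.

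**Step 1. Which planned data could inform tolerability?**

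| Source | Section | What it gives | What it misses |
|---|---|---|---|
| SAEs on the CRF | 8.4.1 to 8.4.3 | Serious events, comparable by arm | All non-serious events |
| Reasons for stopping or withdrawing | 8.4.5 | Stopping, comparable by arm | Anyone with an effect who continues; the listed reasons do not name an adverse event |
| Drug dispensed and returned | 9.4 | Indirect adherence measure | Why doses were not taken; never linked to tolerability |
| Symptom card | 6.1 | Daily scores for 7 days after enrollment | The rest of the course; serves the viral-symptom endpoint |
| Other infections | 4.3, 4.9.2 | Infections present with the CARV infection | Not worded to cover infections arising later on study drug |

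The symptom card covers at most 7/180 = 3.9% of treatment days and leaves at least 173 days uncovered. It runs from enrollment rather than from first dose, so the overlap may be smaller.

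No row covers a non-serious effect in a patient who stays on study drug after the first week.

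**Step 2. Would such events be expected?** The documents give 40 patients randomized 1:1 (Abstract), so n = 20 per arm. They give no event rate, so the rates p below are assumptions.

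P(at least one case in the active arm) = 1 − (1 − p)^20

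- p = 10%: 1 − 0.90^20 = 0.88
- p = 20%: 1 − 0.80^20 = 0.99

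**Step 3. What could a comparison show if the events were recorded?** Two-sided alpha of 0.05 is assumed, as the plan states none. With p̄ the mean of the two rates, the normal approximation is

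power = Φ{ [ |p1 − p0| − 1.96·√(2p̄(1 − p̄)/n) ] / √[ (p1(1 − p1) + p0(1 − p0))/n ] }

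- 5% vs 20%: p̄ = 0.125; (0.15 − 1.96 × 0.1046)/0.1019 = −0.54, so power is about 30%. Exact enumeration with Fisher's test gives 17%.
- 5% vs 40%: p̄ = 0.225; (0.35 − 1.96 × 0.1320)/0.1199 = 0.76, so power is about 78%. Fisher gives 72%.

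One concrete outcome: 4/20 against 1/20 has 5 events in 40 patients. One-sided Fisher p = [C(20,4)·C(20,1) + C(20,5)]/C(40,5) = (96,900 + 15,504)/658,008 = 0.171, and two-sided p = 0.34. The expected count in each event cell is 5 × 20/40 = 2.5, which is small for the chi-squared test that Section 7 would apply.

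Recording would therefore give counts by arm worth describing, but no useful test unless the difference were very large.

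**The case against.** The best defence is that the gap is narrow. It concerns one secondary endpoint in a 40-patient pilot and leaves the primary efficacy analysis untouched. Section 8.4.2 does not say that only SAEs are recorded, and the CRF itself is not among the documents. The extra data would not support a formal test. All of this is fair and limits the weight of the point. It does not supply the missing instruction: the text names no other event to be recorded and no tolerability measure.

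A reader might infer four stronger things that the documents do not support:

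- **That tolerability cannot be compared at all.** The arms can be compared on reasons for stopping (Section 8.4.5) and, indirectly, on returned drug (Section 9.4). Patients who stop study drug stay in follow-up unless they withdraw consent or can no longer take part freely in the consent process.
- **That tolerability belongs to the primary aim.** Section 4.1 names safety alone; tolerability is secondary.
- **That SAEs caused by the drug cannot be told from those caused by the infection or the transplant.** Randomization with a blinded placebo arm balances background events on average, so SAEs can be compared by arm whatever their causality grade.
- **That every SAE must be filed as related,** because Section 8.4.1 has the investigator review SAEs "to determine relationship to the study drug (definitely, likely or possibly related to the study product" and lists no unrelated grade. Section 8.4.3 restricts one reporting duty to related SAEs, which makes sense only if some are judged unrelated. It also requires a report for all SAEs, so no SAE data are lost.

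**Conclusion.** The point holds in a limited form. Apart from discontinuation reasons and drug returns, neither of them designated as the measure, the tolerability endpoint has no stated data source. Non-serious effects in patients who continue study drug have no planned record, and the arms could not be compared on them.

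This is more than missing detail, because following Section 8.4 as written leaves the data uncollected. The textual finding rests on no assumed figure. Its likely size does: the 88% to 99% chance of at least one active-arm case holds for assumed rates of 10% to 20%, and the low power holds for the assumed 5% versus 20%. The plan should be changed, but the primary endpoint is not at risk.

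**What to change.** 1. In Section 8.4.2, have all adverse events, serious and non-serious, recorded on the CRF from first dose to the end of study drug. Collect them at the visits already scheduled for spirometry (Section 6.2) and blood draws (Sections 6.4 and 6.5).
2. In Section 4.9.2, define tolerability by two measures: the proportion of patients with any such event, and the proportion stopping study drug for an adverse event. Make adverse event an explicit reason category on the discontinuation form so that the second can be counted.
3. In Section 7, state that both are summarised descriptively by arm and that the generic chi-squared test is not the basis for conclusions about tolerability.

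The cost is one extra CRF page for 40 patients and a wording change, with no new visit or procedure. The limitation is that with 20 per arm the result will describe tolerability, and similar counts in the two arms would not show that the treatments are tolerated equally well.

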8.4.3. Adverse Event Monitoring and Reporting

Investigators and study staff will follow Federal and local regulations regarding SAE reporting. After randomization, the study staff at each site must report SAEs considered definitely, likely or possibly related to the study medication (as assessed by the study investigator). A study team member will complete an SAE report for all SAE events.

8.4.4. Treatment of Adverse Events

The study staff will handle any AE(s) according to clinical practice. The study personnel will implement treatment procedures and therapy in the best interest of the patient.

8.4.5. Discontinuation of Participants from Treatment

Study participants MUST discontinue study drug for any of the following reasons:

- Withdrawal of informed consent
- Any condition in which, in the opinion of the investigator, indicates that continued study drug treatment is not in the best interest of the patient.
- Termination of the study.
- Ineligibility for continued study drug treatment (Table 1)

Participants who discontinue study drug treatment should still comply with the protocol and undergo the study follow-up procedures, except for those who withdraw informed consent or become unable to freely participate in the ongoing informed consent process. CRF/computer data entry system will capture reason(s) for discontinuation and withdrawal.

9. Study Organization and Administration

9.1. Compliance

Study investigators should conduct the study as described in the protocol. Investigators should not implement deviations or change the protocol except when deemed necessary to eliminate an immediate hazard to a study participant. The investigator must document any significant deviation in the CRF and report the deviation to the IRB.

9.2. Record Keeping and Retention

The investigators must retain copies CRF and source documents for the period required by applicable regulations and guidelines, and institution procedures, whichever is longer.

9.3. Case Report Forms

Investigators and study staff should maintain adequate and accurate records. They should demonstrate consistency of data derived from source documents and CRF data, and they should explain inconsistencies.

9.4. Study Drug Records

The primary investigator at each site has the responsibility to ensure that study personnel (e.g., investigational pharmacist) maintain records of study drug disposition. Records or logs must comply with the applicable regulations and guidelines, and should include:

- Amount received
- Amount stored
- Label identification number or batch number
- Expiration date
- Dates and initials of person responsible for each investigational product inventory entry/movement
- Amount dispensed to and returned by each subject
- Non-study disposition (e.g., lost, wasted, broken)
- Amount returned to manufacturer
- Amount destroyed at study site

